#### **9.7.3 Analyses of Biomarker Endpoints**

Exploratory biomarker analyses beyond those mentioned in this SAP may be conducted by Amgen Clinical Biomarker group.

### **10. Changes From Protocol-specified Analyses**

**Based on the Data Monitoring Committee's recommendation after interim analysis 3 and subsequent decision by the Data Access Plan Team, enrollment in the study was stopped and the study terminated as the study met the pre-specified futility criteria. As such, some analyses that were initially planned in the protocol will not be performed. Key changes from protocol-specified analyses are as follows:**

- Removal of subsequent IAs following study early termination.
- Removal of some exploratory endpoints.
- Removal of statistical comparison of treatment groups at the final analysis; descriptive statistics by treatment groups will be generated instead.

## 12. Appendices

### Appendix A. Reference Values/Toxicity Grades

Assessment of severity for each adverse event and serious adverse event reported during the study will be based on:

The Common Terminology Criteria for Adverse Events (CTCAE), version 5 which is available at the following location:

[http://ctep.cancer.gov/protocolDevelopment/electronic\\_applications/ctc.htm](http://ctep.cancer.gov/protocolDevelopment/electronic_applications/ctc.htm)

### Appendix B. SLE Assessment Forms/Instruments

The hSLEDAI score is computed as sum of the score across the descriptors.

Weight	Score	Descriptor	Definition
8		Seizure	Recent onset, exclude metabolic, infectious or drug causes
8		Psychosis	Altered ability to function in normal activity due to severe disturbance in the perception of reality. Include hallucinations, incoherence, marked loose associations, impoverished thought content, marked illogical thinking, bizarre, disorganized or catatonic behavior. Exclude uremia and drug causes
8		Organic brain syndrome	Altered mental function with impaired orientation, memory, or other intellectual function, with rapid onset and fluctuating clinical features, inability to sustain attention to environment, plus at least two of the following: perceptual disturbance, incoherent speech, insomnia or daytime drowsiness, or increased or decreased psychomotor activity. Exclude metabolic, infection, or drug causes
8		Visual disturbance	Retinal changes of SLE. Include cystoid bodies, retinal hemorrhages, serous exudate or hemorrhages in the choroid, optic neuritis, scleritis or episcleritis. Exclude hypertension, infection, or drug causes
8		Cranial nerve disorder	New onset of sensory or motor neuropathy involving cranial nerves
8		Lupus headache	Severe, persistent headache; may be migrainous, but must be non-responsive to narcotic analgesia.
8		CVA	New onset of cerebrovascular accident(s). Exclude arteriosclerosis
8		Vasculitis	Ulceration, gangrene, tender tender nodules, periungual infarction, splinter hemorrhages, or biopsy or angiogram proof of vasculitis
4		Arthritis	>2 joints of hands and wrists with signs of inflammation (i.e., tenderness with swelling or effusion)

4		Myositis	Proximal muscle aching/weakness, associated with elevated creatinine phosphokinase (CK)/aldolase or EMG changes or a biopsy showing myositis
4		Urinary casts	Heme-granular or RBC casts
4		Hematuria	> 5 RBC/high power field. Exclude stone, infection, or other cause
4		Proteinuria	More than 0.5 gram/24 hours.
4		Pyuria	> 5 WBC/high power field. Exclude infection
2		Rash	Inflammatory type rash.
2		Alopecia	Abnormal, patchy or diffuse loss of hair
2		Mucosal ulcers	Oral or nasal ulcerations
2		Pleurisy	Pleuritic chest pain or pleural rub with effusion or pleural thickening .
2		Pericarditis	Classic pericardial pain and/or rub effusion with ECG confirmation
2		Low complement	Decrease in CH50, C3, or C4 < lower limit of nl for testing laboratory
2		Increased DNA binding	Increased DNA binding above normal range for testing laboratory
1		Fever	> 38 °C. Exclude infectious cause
1		Thrombocytopenia	< 100 x 10  platelets / L, exclude drug causes.
1		Leukopenia	< 3 x 10  WBC/L, exclude drug causes

**BILAG-2004 Index Form**

## BILAG2004 INDEX

Only record items due to SLE Disease Activity & assessment

Scoring: **ND** Not Done  
 1 Improving  
 2 Same  
 3 Worse  
 4 New  
 Yes/No OR Value (where indicated)  
 indicate if not due to SLE activity  
 (default is 0 = not present)

### CONSTITUTIONAL

1. Pyrexia - documented > 37.5°C ( )  
 2. Weight loss - unintentional > 5% ( )  
 3. Lymphadenopathy/splenomegaly ( )  
 4. Anorexia ( )

### MUCOCUTANEOUS

5. Skin eruption - severe ( )  
 6. Skin eruption - mild ( )  
 7. Angio-oedema - severe ( )  
 8. Angio-oedema - mild ( )  
 9. Mucosal ulceration - severe ( )  
 10. Mucosal ulceration - mild ( )  
 11. Panniculitis/Bullous lupus - severe ( )  
 12. Panniculitis/Bullous lupus - mild ( )  
 13. Major cutaneous vasculitis/thrombosis ( )  
 14. Digital infarcts or nodular vasculitis ( )  
 15. Alopecia - severe ( )  
 16. Alopecia - mild ( )  
 17. Peri-ungual erythema/chilblains ( )  
 18. Splinter haemorrhages ( )

### NEUROPSYCHIATRIC

19. Aseptic meningitis ( )  
 20. Cerebral vasculitis ( )  
 21. Demyelinating syndrome ( )  
 22. Myelopathy ( )  
 23. Acute confusional state ( )  
 24. Psychosis ( )  
 25. Acute inflammatory demyelinating polyradiculoneuropathy ( )  
 26. Mononeuropathy (single/multiplex) ( )  
 27. Cranial neuropathy ( )  
 28. Plexopathy ( )  
 29. Polyneuropathy ( )  
 30. Seizure disorder ( )  
 31. Status epilepticus ( )  
 32. Cerebrovascular disease (not due to vasculitis) ( )  
 33. Cognitive dysfunction ( )  
 34. Movement disorder ( )  
 35. Autonomic disorder ( )  
 36. Cerebellar ataxia (isolated) ( )  
 37. Lupus headache - severe unrelenting ( )  
 38. Headache from IC hypertension ( )

### MUSCULOSKELETAL

39. Myositis - severe ( )  
 40. Myositis - mild ( )  
 41. Arthritis (severe) ( )  
 42. Arthritis (moderate)/Tendonitis/Tenosynovitis ( )  
 43. Arthritis (mild)/Arthralgia/Myalgia ( )

Weight (kg): \_\_\_\_\_

### CARDIORESPIRATORY

44. Myocarditis - mild ( )  
 45. Myocarditis/Endocarditis + Cardiac failure ( )  
 46. Arrhythmia ( )  
 47. New valvular dysfunction ( )  
 48. Pleurisy/Percarditis ( )  
 49. Cardiac tamponade ( )  
 50. Pleural effusion with dyspnoea ( )  
 51. Pulmonary haemorrhage/vasculitis ( )  
 52. Intestinal alveolitis/pneumonitis ( )  
 53. Shrinking lung syndrome ( )  
 54. Aortitis ( )  
 55. Coronary vasculitis ( )

### GASTROINTESTINAL

56. Lupus peritonitis ( )  
 57. Abdominal serositis or ascites ( )  
 58. Lupus enteritis/colitis ( )  
 59. Malabsorption ( )  
 60. Protein losing enteropathy ( )  
 61. Intestinal pseudo-obstruction ( )  
 62. Lupus hepatitis ( )  
 63. Acute lupus cholecystitis ( )  
 64. Acute lupus pancreatitis ( )

### OPHTHALMIC

65. Orbital inflammation/myositis/proptosis ( )  
 66. Keratitis - severe ( )  
 67. Keratitis - mild ( )  
 68. Anterior uveitis ( )  
 69. Posterior uveitis/retinal vasculitis - severe ( )  
 70. Posterior uveitis/retinal vasculitis - mild ( )  
 71. Episcleritis ( )  
 72. Scleritis - severe ( )  
 73. Scleritis - mild ( )  
 74. Retinal/choroidal vaso-occlusive disease ( )  
 75. Isolated cotton-wool spots (cytoid bodies) ( )  
 76. Optic neuritis ( )  
 77. Anterior ischaemic optic neuropathy ( )

### RENAL

78. Systolic blood pressure (mm Hg) value ( )   
 79. Diastolic blood pressure (mm Hg) value ( )   
 80. Accelerated hypertension Yes/No ( )  
 81. Urine dipstick protein (+=1, ++=2, +++=3) ( )  
 82. Urine albumin-creatinine ratio mg/mmol ( )  
 83. Urine protein-creatinine ratio mg/mmol ( )  
 84. 24 hour urine protein (g) value ( )   
 85. Nephrotic syndrome Yes/No ( )  
 86. Creatinine (plasma/serum)  $\mu$ mol/l ( )  
 87. GFR (calculated) ml/min/1.73 m^2 ( )  
 88. Active urinary sediment Yes/No ( )  
 89. Active nephritis Yes/No ( )

### HAEMATOLOGICAL

90. Haemoglobin (g/dl) value ( )   
 91. Total white cell count ( $\times 10^9/l$ ) value ( )   
 92. Neutrophils ( $\times 10^9/l$ ) value ( )   
 93. Lymphocytes ( $\times 10^9/l$ ) value ( )   
 94. Platelets ( $\times 10^9/l$ ) value ( )   
 95. TTP ( )  
 96. Evidence of active haemolysis Yes/No ( )  
 97. Coombs' test positive (isolated) Yes/No ( )

Revision: 12/Jan/2007

Investigator initials: \_\_\_\_\_ Date of assessment: \_\_\_\_\_

## BILAG-2004 INDEX SCORING

- scoring based on the principle of physician's intention to treat

Category	Definition
A	Severe disease activity requiring any of the following treatment: 1. systemic high dose oral glucocorticoids (equivalent to prednisolone > 20 mg/day)

	2. intravenous pulse glucocorticoids (equivalent to pulse methylprednisolone $\geq$ 500 mg) 3. systemic immunomodulators (include biologicals, immunoglobulins and plasmapheresis) 4. therapeutic high dose anticoagulation in the presence of high dose steroids or immunomodulators e.g.: warfarin with target INR 3 - 4
B	Moderate disease activity requiring any of the following treatment: 1. systemic low dose oral glucocorticoids (equivalent to prednisolone $\leq$ 20 mg/day) 2. intramuscular or intra-articular or soft tissue glucocorticoids injection (equivalent to methylprednisolone $<$ 500mg) 3. topical glucocorticoids 4. topical immunomodulators 5. antimalarials or thalidomide or prasterone or acitretin 6. symptomatic therapy e.g.: NSAIDs for inflammatory arthritis
C	Mild disease
D	Inactive disease but previously affected
E	System never involved

#### **BILAG Constitutional Scoring Algorithm**

Grade	Criteria
A	1. Pyrexia recorded as 2 (same), 3 (worse) or 4 (new) AND 2. Any 2 or more of the following recorded as 2 (same), 3 (worse) or 4 (new): a) Weight loss b) Lymphadenopathy/splenomegaly c) Anorexia
B	1. Pyrexia recorded as 2 (same), 3 (worse) or 4 (new) OR 2. Any 2 or more of the following recorded as 2 (same), 3 (worse) or 4 (new): a) Weight loss b) Lymphadenopathy/splenomegaly c) Anorexia 3. BUT do not fulfil criteria for Category A
C	1. Pyrexia recorded as 1 (improving) OR 2. One or more of the following recorded as $> 0$ : a) Weight loss b) Lymphadenopathy/Splenomegaly c) Anorexia

	3. BUT does not fulfil criteria for category A or B
D	Previous involvement (i.e. A, B, C or D domain grade at any previous visits or domain previous involvement is yes)
E	No previous involvement
Missing	

### **BILAG Mucocutaneous Scoring Algorithm**

Grade	Criteria
A	Any of the following recorded as 2 (same), 3 (worse) or 4 (new): a) Skin eruption - severe b) Angio-oedema - severe c) Mucosal ulceration - severe d) Panniculitis/Bullous lupus - severe e) Major cutaneous vasculitis/thrombosis
B	1. Any Category A features recorded as 1 (improving) OR 2. Any of the following recorded as 2 (same), 3 (worse) or 4 (new): 1. Skin eruption - mild 2. Panniculitis/Bullous lupus - mild 3. Digital infarcts or nodular vasculitis 4. Alopecia - severe
C	a) Any Category B features recorded as 1 (improving) OR b) Any of the following recorded as > 0: a) Angio-oedema - mild b) Mucosal ulceration - mild c) Alopecia - mild d) Periungual erythema/chilblains e) Splinter haemorrhages
D	Previous involvement (i.e. A, B, C or D domain grade at any previous visits or domain previous involvement is yes)
E	No previous involvement
Missing	

### **BILAG Neuropsychiatric Scoring Algorithm**

Grade	Criteria
A	Any of the following recorded as 2 (same), 3 (worse) or 4 (new): 1. Aseptic meningitis 2. Cerebral vasculitis 3. Demyelinating syndrome 4. Myelopathy 5. Acute confusional state 6. Psychosis 7. Acute inflammatory demyelinating polyradiculoneuropathy 8. Mononeuropathy (single/multiplex) 9. Cranial neuropathy 10. Plexopathy

	11. Polyneuropathy 12. Status epilepticus 13. Cerebellar ataxia
B	a) Any Category A features recorded as 1 (improving) OR b) Any of the following recorded as 2 (same), 3 (worse) or 4 (new): a) Seizure disorder b) Cerebrovascular disease (not due to vasculitis) c) Cognitive dysfunction d) Movement disorder e) Autonomic disorder f) Lupus headache - severe unrelenting g) Headache due to raised intracranial hypertension
C	Any Category B features recorded as 1 (improving)
D	Previous involvement (i.e. A, B, C or D domain grade at any previous visits or domain previous involvement is yes)
E	No previous involvement
Missing	

### **BILAG Musculoskeletal Scoring Algorithm**

Grade	Criteria
A	Any of the following recorded as 2 (same), 3 (worse) or 4 (new): a) Severe Myositis b) Severe Arthritis
B	1. Any Category A features recorded as 1 (improving) OR 2. Any of the following recorded as 2 (same), 3 (worse) or 4 (new): a) Mild Myositis b) Moderate Arthritis/Tendonitis/Tenosynovitis
C	1. Any Category B features recorded as 1 (improving) OR 2. Any of the following recorded as > 0: a) Mild Arthritis/Arthralgia/Myalgia
D	Previous involvement (i.e. A, B, C or D domain grade at any previous visits or domain previous involvement is yes)
E	No previous involvement
Missing	

### **BILAG Cardiorespiratory Scoring Algorithm**

Grade	Criteria
A	Any of the following recorded as 2 (same), 3 (worse) or 4 (new): a) Myocarditis/Endocarditis + Cardiac failure b) Arrhythmia c) New valvular dysfunction

	

d) Cardiac tamponade

e) Pleural effusion with dyspnoea

f) Pulmonary haemorrhage/vasculitis

g) Interstitial alveolitis/pneumonitis

h) Shrinking lung syndrome

i) Aortitis

j) Coronary vasculitis

B	

1. Any Category A features recorded as 1 (improving) OR

2. Any of the following recorded as 2 (same), 3 (worse) or 4 (new):

a) Pleurisy/Pericarditis

b) Myocarditis - mild

C	Any Category B features recorded as 1 (improving)
D	Previous involvement (i.e. A, B, C or D domain grade at any previous visits or domain previous involvement is yes)
E	No previous involvement
Missing	

### **BILAG Gastrointestinal Scoring Algorithm**

Grade	Criteria
A	Any of the following recorded as 2 (same), 3 (worse) or 4 (new): 

a) Peritonitis

b) Lupus enteritis/colitis

c) Intestinal pseudo-obstruction

d) Acute lupus cholecystitis

e) Acute lupus pancreatitis

B	

1. Any Category A feature recorded as 1 (improving) OR

2. Any of the following recorded as 2 (same), 3 (worse) or 4 (new):

a) Abdominal serositis and/or ascites

b) Malabsorption

c) Protein losing enteropathy

d) Lupus hepatitis

C	Any Category B features recorded as 1 (improving)
D	Previous involvement (i.e. A, B, C or D domain grade at any previous visits or domain previous involvement is yes)
E	No previous involvement
Missing	

### **BILAG Ophthalmic Scoring Algorithm**

Grade	Criteria
A	Any of the following recorded as 2 (same), 3 (worse) or 4 (new): 
 
a) Orbital inflammation/myositis/proptosis
 
b) Keratitis - severe
 
c) Posterior uveitis/retinal vasculitis - severe
 
d) Scleritis - severe
 
e) Retinal/choroidal vaso-occlusive disease
 
f) Optic neuritis
 
g) Anterior ischaemic optic neuropathy
 

B	1. Any Category A features recorded as 1 (improving) OR 2. Any of the following recorded as 2 (same), 3 (worse) or 4 (new): 
 
a) Keratitis - mild
 
b) Anterior uveitis
 
c) Posterior uveitis/retinal vasculitis - mild
 
d) Scleritis - mild
 

C	1. Any Category B features recorded as 1 (improving) OR 2. Any of the following recorded as > 0: 
 
a) Episcleritis
 
b) Isolated cotton-wool spots (cystoid bodies)
 

D	Previous involvement (i.e. A, B, C or D domain grade at any previous visits or domain previous involvement is yes)
E	No previous involvement
Missing	

### BILAG Renal Scoring Algorithm

Grade	Criteria
A	Two or more of the following providing 1, 4 or 5 is included: 
 
1. Deteriorating proteinuria (severe) defined as               
 
a) urine dipstick increased by <math>\geq 2</math> levels (used only if other methods of urine protein estimation not available); or
 
b) 24-hour urine protein <math>> 1</math> g that has not decreased (improved) by <math>\geq 25\%</math>; or
 
c) urine protein-creatinine ratio <math>> 100</math> mg/mmol that has not decreased (improved) by <math>\geq 25\%</math>; or
 
d) urine albumin-creatinine ratio <math>> 100</math> mg/mmol that has not decreased (improved) by <math>\geq 25\%</math>
 
 
 
2. Accelerated hypertension
 
3. Deteriorating renal function (severe) defined as               
 
a) plasma creatinine <math>> 130</math> <math>\mu\text{mol/l}</math> and having risen to <math>> 130\%</math> of previous value; or
 
b) GFR <math>< 80</math> ml/min per <math>1.73\text{ m}^2</math> and having fallen to <math>< 67\%</math> of previous value; or
 
c) GFR <math>< 50</math> ml/min per <math>1.73\text{ m}^2</math>, and last time was <math>> 50</math> ml/min per <math>1.73\text{ m}^2</math> or was not measured.
 
 
 

	4. Active urinary sediment 5. Histological evidence of active nephritis within last 3 months 6. Nephrotic syndrome
B	One of the following: 1. One of the Category A feature 2. Proteinuria (that has not fulfilled Category A criteria) a) urine dipstick which has risen by 1 level to at least 2+ (used only if other methods of urine protein estimation not available); or b) 24-hour urine protein $\geq 0.5$ g that has not decreased (improved) by $\geq 25\%$ ; or c) urine protein-creatinine ratio $\geq 50$ mg/mmol that has not decreased (improved) by $\geq 25\%$ ; or d) urine albumin-creatinine ratio $\geq 50$ mg/mmol that has not decreased (improved) by $\geq 25\%$ 3. Plasma creatinine $> 130$ $\mu\text{mol/l}$ and having risen to $\geq 115\%$ but $\leq 130\%$ of previous value
C	One of the following: 1. Mild/Stable proteinuria defined as a) urine dipstick $\geq 1+$ but has not fulfilled criteria for Category A & B (used only if other methods of urine protein estimation not available); or b) 24 hour urine protein $> 0.25$ g but has not fulfilled criteria for Category A & B; or c) urine protein-creatinine ratio $> 25$ mg/mmol but has not fulfilled criteria for Category A & B; or d) urine albumin-creatinine ratio $> 25$ mg/mmol but has not fulfilled criteria for Category A & B 2. Rising blood pressure (providing the recorded values are $> 140/90$ mm Hg) which has not fulfilled criteria for Category A & B, defined as a) systolic rise of $\geq 30$ mm Hg; and b) diastolic rise of $\geq 15$ mm Hg
D	Previous involvement (i.e. A, B, C or D domain grade at any previous visits or domain previous involvement is yes)
E	No previous involvement
Missing	

Since the urine albumin-creatinine ratio and 24-hour urine protein are not collected in this study, the criteria for BILAG proteinuria will be based on urine dipstick and urine protein-creatinine ratio only.

### **BILAG Hematological Scoring Algorithm**

Grade	Criteria
A	1. TTP recorded as 2 (same), 3 (worse) or 4 (new) or 2. Any of the following: a) Evidence of haemolysis and Haemoglobin $< 8$ g/dl

	b) Platelet count $< 25 \times 10^9/l$
B	
 
1. TTP recorded as 1 (improving) or
 
2. Any of the following:           
 
a) Evidence of haemolysis and Haemoglobin 8 - 9.9 g/dl
 
b) Haemoglobin <math>< 8 \text{ g/dl}</math> (without haemolysis)
 
c) White cell count <math>< 1.0 \times 10^9/l</math>
 
d) Neutrophil count <math>< 0.5 \times 10^9/l</math>
 
e) Platelet count <math>25 - 49 \times 10^9/l</math>
 
 
 

C	Any of the following: 
 
a) Evidence of haemolysis and Haemoglobin <math>\geq 10 \text{ g/dl}</math>
 
b) Haemoglobin <math>8 - 10.9 \text{ g/dl}</math> (without haemolysis)
 
c) White cell count <math>1 - 3.9 \times 10^9/l</math>
 
d) Neutrophil count <math>0.5 - 1.9 \times 10^9/l</math>
 
e) Lymphocyte count <math>< 1.0 \times 10^9/l</math>
 
f) Platelet count <math>50 - 149 \times 10^9/l</math>
 
g) Isolated Coombs' test positive
 

D	Previous involvement (i.e. A, B, C or D domain grade at any previous visits or domain previous involvement is yes)
E	No previous Involvement.
Missing	

## LLDAS

Criteria	Derivation
HSLEDAI $\leq 4$ with no activity in major organ systems (renal, CNS, cardiopulmonary, vasculitis, fever)	HSLEDAI score $\leq 4$  proteinuria, haematuria, pyuria, urinary casts, seizure, psychosis, organic brain syndrome, cranial nerve disorder, CVA, pericarditis, pleurisy, vasculitis and fever in hSLEDAI are marked 'not present'
No new lupus activity compared with the previous assessment	No new 'present' hSLEDAI descriptors compared to previous visit
PGA $\leq 1$	PGA $\leq 1$

Current prednisolone (or equivalent) dose $\leq$ 7.5 mg/day	Prednisone equivalent is $\leq$ 7.5 mg/day at the visit
Standard maintenance doses of immunosuppressive drugs and approved biological agents (i.e. no increase or initiation of immunosuppressive drugs.)	No new or increase in immunosuppressant at the visit

## Appendix C. Patient-reported Outcome Forms/Instruments

### C1. SF-36 Version 2

SF-36 items will be scored using the SF-36 version 2.0 Quality Metric Health Outcome Scoring Software (Ware et al, 2007).

### C2. Scoring algorithm for PROMIS Fatigue SF 7A

PROMIS SF v1.0 – Fatigue 7A will be scored according to the PROMIS Fatigue Brief Guide including the scoring in the Instrument Section downloaded from

[http://www.healthmeasures.net/images/PROMIS/manuals/PROMIS\\_Fatigue\\_Scoring\\_Manual.pdf](http://www.healthmeasures.net/images/PROMIS/manuals/PROMIS_Fatigue_Scoring_Manual.pdf) on 28 Feb 2019.

**To calculate the score for PROMIS Fatigue SF 7A, sum the values of the responses to each of the 7 questions. The lowest and highest possible sum is 7 and 35, respectively. Then, use the table below to rescale the score into a standardize score with a mean of 50 and a standard deviation of 10.**

Conversion Table	
Raw score	T-score
7	29.4
8	33.4
9	36.9
10	39.6
11	41.9
12	43.9
13	45.8
14	47.6
15	49.2
16	50.8
17	52.2
18	53.7
19	55.1
20	56.4
21	57.8
22	59.2
23	60.6
24	62.0
25	63.4

26	64.8
27	66.3
28	67.8
29	69.4
30	71.1
31	72.9
32	74.8
33	77.1
34	79.8
35	83.2

### C3. Scoring algorithm for Modified LupusQoL

The LupusQoL will be scored using the scoring algorithm from the RWS Life Science website accessed 10 April 2020. <http://www.corptransinc.com/sites/lupusqol/instrument-information/instrument-scoring>

**To compute the LupusQOL raw domain score, sum the values of the responses to each question by domain based on the tables below and divide by the number of items. Then, transform the raw domain score by dividing by 4 and multiplying by 100.**

Item Response	All the time	Most of the time	A good bit of the time	Occasionally	Never	Not applicable
Score	0	1	2	3	4	Do not score

Domain	Number of Items	Item Numbers
Physical Health	8	1-8
Pain	3	9-11
Planning	3	12-14
Intimate Relationship	2	15, 16
Burden to Others	3	17-19
Emotional Health	6	20-25
Body Image	5	36-30
Fatigue	4	31-34

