### **LupusQoL Score**

The LupusQoL is the US version of the 34-item PRO originally developed in the United Kingdom (McElhone et al, 2007) for use in adults. This is a SLE-specific health-related quality of life instrument. The LupusQoL consists of 8 domains: physical health (8 items), pain (3 items), planning (3 items), intimate relationships (2 items), burden to others (3 items), emotional health (6 items), body image (5 items), and fatigue (4 items). The final instrument has demonstrated good internal reliability (Cronbach's 0.88 to 0.95), good test-retest reliability ( $r$  0.72 to 0.93), good concurrent validity with the comparable domains of the SF-36 ( $r$  0.71 to 0.79) and good discriminant validity for different levels of disease activity, measured by BILAG index, and damage (Systemic Lupus International Collaborating Clinics/ACR damage index) but not for all domains. The instrument also has acceptable ceiling effects and minimal floor effects.

Details of the scoring algorithm are described in [Appendix C](#).

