### 8.3 Handling of Missing and Incomplete Data

Subjects may have missing specific data points for a variety of reasons. In general, data may be missing due to a subject's early withdrawal from study, a missed visit, or non-evaluability of a specific clinical or laboratory measurement at its planned clinical visit.

**Additionally, as the study was terminated before the planned completion, subjects may have missed clinical visits including not completing the week 52 visit. For efficacy and PRO outcomes, subjects who terminated early due to sponsor decision will be excluded from analyses of data from visits for which they did not have the opportunity to participate in by the date of study termination decision being communicated to sites, i.e. April 5, 2023. Efficacy data collected after this date will be censored and excluded from analyses for that particular visit.** Unless specified, no imputation will be used. The general procedures outlined below describe what will be done when a data point is missing.

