**Table 9-2. Secondary Efficacy Endpoint Summary Table**

Endpoint	Primary Summary and Analysis Method

• BICLA response at week 52

• LLDAS response at week 52

• Reduction of OCS to <math>\leq 7.5</math> mg/day by week 44 and sustained through week 52 in subjects with a baseline OCS dose <math>\geq 10</math> mg/day

• SRI-4 response at week 24

• BICLA response at week 24

• HSLEDAI reduction <math>\geq 4</math> points from baseline at week 24

• HSLEDAI reduction <math>\geq 4</math> points from baseline at week 52

	Number and percentage of subjects achieving response of interest will be summarized by randomized treatment arm.

• Improvement from baseline in tender and swollen joint count <math>\geq 50\%</math> at weeks 8, 12, 24, 36, and 52 in subjects with <math>\geq 6</math> tender and swollen joints involving the hands and wrists at baseline

• CLASI activity score <math>\geq 50\%</math> improvement from baseline at week 12, 24, 36, and 52 in subjects with a CLASI activity score <math>\geq 8</math> at baseline

	Number and percentage of subjects achieving response of interest will be summarized by randomized treatment arm.

• Annualized flare rate (as measured by BILAG score designation of “worse” or “new” resulting in a B score in <math>\geq 2</math> organs or an A score in <math>\geq 1</math> organ) over 52 weeks

	Descriptive statistics will be summarized by randomized treatment arm.

• Change from baseline in fatigue standardized score using the PROMIS Fatigue SF 7a at week 12, 24, 36, and 52

• Change from baseline in the physical component score, mental

	Descriptive statistics will be summarized by randomized treatment arm.

component score and individual domains of the SF 36 v2 at week 12, 24, 36, and 52	
• Change from baseline in the domain scores on the Lupus QoL at weeks 12, 24, 36, and 52	

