**antibody (anticardiolipin antibody IgG and IgM, beta-2 glycoprotein IgG and IgM and lupus anticoagulant).**

#### **9.7.2 Analyses of Clinical Outcome Assessments**

The PRO endpoints include fatigue standardized score using PROMIS Fatigue SF 7, physical and mental component score and individual domains of the SF 36 v2.

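### Does the LupusQoL formula in SAP Appendix C3 score a 'Not applicable' answer as the worst response?

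*SAP*

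**What the plan says.** SAP Section 5.7, under LupusQoL Score, lists eight domains totalling 34 items and passes the scoring to Appendix C: "Details of the scoring algorithm are described in" that appendix. Appendix C3 opens by naming its source: "The LupusQoL will be scored using the scoring algorithm from the RWS Life Science website accessed 10 April 2020". It then gives a short form of the calculation. For the raw domain score, the analyst is to "sum the values of the responses to each question by domain based on the tables below and divide by the number of items". The rescaling step is: "Then, transform the raw domain score by dividing by 4 and multiplying by 100".

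Two tables follow. The response table runs from 0 (the symptom is present all the time) to 4 (never), so a higher score is better. It has a separate 'Not applicable' column marked as not to be scored. The domain table has a column headed 'Number of Items' with counts from 2 to 8.

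SAP Section 8.3 has no LupusQoL rule, only the general default: "Unless specified, no imputation will be used". The endpoint in SAP Table 9-2 is "Change from baseline in the domain scores on the Lupus QoL at weeks 12, 24, 36, and 52", summarised by arm with descriptive statistics.

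**The concern.** The formula's divisor has the same name as a table column that holds fixed counts. Read that way, an unscored item adds nothing to the sum but still counts in the denominator. That gives the same score as answering that the symptom is present all the time, which is the worst response. A domain in which every item is 'Not applicable' could then be computed as 0, the bottom of the scale, instead of being missing.

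The two-item Intimate Relationship domain is the most sensitive. If two analysts chose different divisors they would report different domain scores, and possibly different numbers of subjects summarised, for a listed secondary endpoint. The other places one might look do not help. Section 8.3 gives specific rules for hSLEDAI, CLASI, BILAG, PGA and joint counts but none for this instrument. Section 9.7.2, which begins "The PRO endpoints include fatigue standardized score using PROMIS Fatigue SF 7", does not mention LupusQoL. The protocol's LupusQoL section describes the instrument without a scoring rule.

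The same table also prints the Body Image items as 36-30, which is not a possible range.

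**Working it through.** **Inputs, all from Appendix C3.** Response values 0 to 4. Items per domain n: Physical Health 8, Pain 3, Planning 3, Intimate Relationship 2, Burden to Others 3, Emotional Health 6, Body Image 5, Fatigue 4.

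**The plan's own figure.** 8 + 3 + 3 + 2 + 3 + 6 + 5 + 4 = 34, which agrees with the 34 items stated in Section 5.7.

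**The item range.** The printed ranges are 1-8, 9-11, 12-14, 15-16, 17-19, 20-25 and 31-34. The numbers left over are 26 to 30, which is five items and matches the Body Image count. So 36-30 is a misprint for 26-30.

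**Two readings of the divisor.** Let S be the sum of scored responses and k the number of items scored.

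- Fixed count: score = S / n / 4 × 100.
- Scored items: score = S / k / 4 × 100.

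With one 'Not applicable' item, k = n − 1. If the scored-item reading gives m, the fixed-count reading gives m(n − 1)/n, so the gap is m/n.

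| Domain | n | Gap at m = 50 | Gap at m = 100 |
|---|---|---|---|
| Intimate Relationship | 2 | 25.0 | 50.0 |
| Pain, Planning, Burden to Others | 3 | 16.7 | 33.3 |
| Fatigue | 4 | 12.5 | 25.0 |
| Body Image | 5 | 10.0 | 20.0 |
| Emotional Health | 6 | 8.3 | 16.7 |
| Physical Health | 8 | 6.25 | 12.5 |

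The gap is 0 when m = 0. Under the fixed count, a 'Not applicable' item and a response of 0 leave both S and n the same, so they score alike in all eight domains.

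**A change score.** Intimate Relationship, both items answered 3 at baseline: (3 + 3)/2/4 × 100 = 75. Later one item is 3 and the other 'Not applicable'.

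- Fixed count: 3/2/4 × 100 = 37.5, a change of −37.5.
- Scored items: 3/1/4 × 100 = 75, a change of 0.

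**An empty domain.** The scored-item reading gives 0/0, which is missing. The fixed count gives 0/n = 0 only if the sum of no scored responses is taken as 0. Appendix C3 does not say so, and a program could return missing instead.

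**Which reading the text supports.** The sum is to be formed from the tables, and the response table says not to score the item. Counting it in the divisor gives it the value 0, which amounts to imputing the worst answer. That conflicts both with the instruction not to score and with the default in Section 8.3. The scored-item divisor conflicts with neither.

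**The case for a change.** The best argument for a change is that the SAP shows elsewhere how such a rule is written. For joint counts, Section 8.3 divides by the joints evaluated, requires at least half to be evaluable, and sets the count to missing below that. Appendix C3 has no counterpart to any of these three elements, and its wording matches a column of fixed numbers. A secondary endpoint should be reproducible from the SAP, and a clarification would cost only a line or two.

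Part of this stands. The printed text is silent on the divisor, on any minimum number of answered items and on the empty domain, and the m/n arithmetic is right. It does not follow that analysts are left without a rule. Appendix C3 first adopts a named algorithm and then condenses it; C1 and C2 likewise rely on external scoring sources. That algorithm's text is not in the documents, so it cannot be shown to settle the divisor or to leave it open. The joint-count rule also counts against the fixed-count reading, because where the SAP does address unevaluable components it divides by what was evaluated.

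The large figures are worst cases. The 50-point gap needs the two-item domain with the other answer at the top of the scale. The questionnaire is not reproduced, so it is not known which items offer 'Not applicable'.

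**Conclusion.** No change to the plan follows. Appendix C3 leaves out a detail that an analyst using the cited algorithm, the instruction not to score and the no-imputation default would fill sensibly by dividing by the items scored and leaving an empty domain missing. The Body Image range is a clerical slip that the neighbouring rows and the five-item count resolve.

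If the fixed count were used, the effect for a subject with one 'Not applicable' item would be m/n points on that domain: 6.25 to 25.0 at m = 50 and at most 12.5 to 50.0, depending on domain size. That is a hypothetical per-subject figure. Nothing in the documents shows that the program scores this way, and without the frequency of 'Not applicable' answers no effect on an arm mean or a difference between arms can be claimed.

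The consequence is also bounded by what remains of the analysis. SAP Section 10 removes the treatment comparisons after the futility stop: "descriptive statistics by treatment groups will be generated instead". The futility rule used SRI-4, so no test, error rate or decision depends on LupusQoL scores. This conclusion assumes that the cited algorithm does not itself prescribe the fixed count, which cannot be checked from the documents.
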